7.4 Interim Analysis

Part I

A final analysis will be conducted after all

subjects complete Part I.

Part II

In Part II, an administrative IA may be performed. If an IA is performed, the study will continue as planned in a masked fashion.

CONFIDENTIAL

7.5 Adjustment for Multiplicity

Part I

This is the dose-escalation part of the study to identify the MTD based on the evaluation of the benefit-risk without any formal statistical comparison. Adjustment for multiplicity is, therefore not applicable.

Part II

The primary efficacy endpoint of Part II is defined as the proportion of study eyes with \geq 7 dB improvement from baseline at \geq 5 of the 16 central loci of the 10-2 grid assessed by MAIA microperimetry at 12 months.

At final analysis, the primary endpoint will be tested byHochberg's (Hochberg 1988) step-up method with familywise error rate controlled at right-sided 0.10. The high dose vs. control group, and the low dose vs. control group will be tested respectively. The study will be declared positive if either dose or both doses achieve statistical significance.

Two hypotheses will be tested for primary endpoint:

High dose vs control group:

 $H_0: p_{trt} = p_{untr} \ versus \ H_1: p_{trt} > p_{untr}$

Low dose vs control group:

H₀: $p_{trt} = p_{untr}$ versus H₁: $p_{trt} > p_{untr}$

The algorithm is based on data-driven ordering of hypotheses $H_{(1)}$ and $H_{(2)}$ corresponding to the ordered p-values $P_{(1)} < P_{(2)}$.

Step 1: start with larger p-value $P_{(2)}$. If $P_{(2)} < 0.10$ (one-sided) then reject null hypotheses and claim this test is significant. The remaining hypothesis test is also rejected. Both doses achieve statistical significance. Otherwise if $P_{(2)} \ge 0.10$ this is not significant and proceed to the next test to compare $P_{(1)}$ with 0.05 (one-sided).

Step 2: if $P_{(1)} < 0.05$ (one-sided) then testing stops. The dose associated with $P_{(1)}$ is claimed statistically significant than control group. The dose associated with $P_{(2)}$ is not statistically significant. Or if $P_{(1)} \ge 0.05$ (one-sided) then testing stops and both doses are not statistically significant.

7.5 Imputation of Partial Dates for Adverse Events and Concomitant Medication

| iniputation | | | | | | | |
|----------------------------|---------------|--|--|--|--|--|--|
| | Missing | Condition | Imputed Value | | | | |
| Start date | Day | The event started in the same year and month as Study Day 1 (or treatment period start date) | Study Day 1 (or treatment period start date) | | | | |
| (AE, | | Otherwise | 01 | | | | |
| concomitant medication) | Day and month | The event started in the same year as Study Day 1 (or treatment period start date) | Study Day 1 (or treatment period start date) | | | | |

For on-study adverse events and concomitant medications with partially missing dates, the imputation rule is tabulated as follows.

| | | Otherwise | 01JAN |
|-------------------------|---|--|---|
| | Completely m | issing (missing day, month, and year) | No imputation will be performed |
| | Day | The event stopped in the same year and month as the End of Study date | The End of Study date or the analysis data cut-off date |
| Stop date (AE, | | Otherwise | The last day of the month |
| concomitant medication) | Day and month | The event stopped in the same year as the End of Study date | The End of Study date or the analysis data cut-off date |
| | | Otherwise | 31DEC |
| | Completely missing (missing day, month, and year) | | No imputation will be performed |

7.6 Handling of Missing Data and Extreme Outliers

The number, pattern and timing of missing data will be examined along with the reasons for withdrawal or for missing data.

All reasonable efforts will be made to obtain complete data for both eyes on all subjects. However misisng observations may occur. In addition, due to the impact of coronavirus disease 2019 (COVID-19) on the ongoing trial, some assessments might be missed or delayed.

In Part I, although the visit will still be considered out-of-window, if subjects are unable to attend the 24-month visit during the protocol-defined window, they should return to the site to complete this visit as soon as it is possible for them to do so. This will be considered their 24-month visit. For efficacy endpoints, observations collected within 6 months of the last visit window will be included in analysis. Safety endpoints will be analyzed on observed data and no imputation will be performed. All analysis in Part I will be generated by descriptive statistics.

In Part II, although the visit will still be considered out-of-window, if subjects are unable to attend the 12-month visit during the protocol-defined window, they should return to the site to complete this visit as soon as it is possible for them to do so. This will be considered their 12-month visit. For efficacy endpoints, observations collected within 6 months of the last visit window will be included in analysis. Additional imputation approaches for the primary endpoint and selected secondary endpoints will be also implemented.

Safety analyses will be descriptive only and will be performed using the 'observed case' (OC) method. No missing data imputation will be applied to safety analyses.

The 3*IQR rule method will be used to identify the extreme outliers for the mean sensitivity. A data point is an extreme outlier if it is more than 3*IQR above the third quartile (Q3) or below the first quartile (Q1) where IQR, the interquartile range, is calculated as the absolute difference between Q3 and Q1. The influence of the extreme outliers will be investigated. The extreme outliers may be excluded from the analysis based on statistical and clinical evaluation. See section 7.12.2 on handling patients with data identified with extreme outliers in mean sensitivity analysis.

7.7 Disposition of Subjects

Part I

Accounting of subjects will include number of subjects in Safety Analysis Set, number (%) of subjects who attended each visit, number (%) of subjects who completed the study, and number (%) of subjects who discontinued from study. For subjects who discontinued from study early, the reasons for discontinuation will be summarized.

Part II

Accounting of subjects will include number of subjects randomized, number of subjects in Safety Analysis Set and ITT Analysis Set, number (%) of subjects who attend each visit, number (%) of subjects who completed the study, and number (%) of subjects who discontinued from study. For subjects who discontinued from study, the reasons for discontinuation will be summarized.

7.8 Demographic and Baseline Characteristics

Demographic of age, gender, ethnicity, race will be summarized by each treatment group in the Safety Analysis Set.

Baseline ocular characteristics including mean sensitivity, LLVA, BCVA, fundus autofluorescence (FAF),

, central ellipsoid area, central horizontal ellipsoid width, intraocular pressure, and Pelli-Robson contrast sensitivity will be summarized by treatment groups (except), visits and eyes in the Safety Analysis Set. Listings for demographics and baseline characteristics will be provided.

7.9 Medical and Ocular History

Medical and ocular history will be coded using the Medical Dictionary for Regulatory Activities (MedDRA) Version 23.1.

Ocular history will be summarized by System Organ Class (SOC) and Preferred Term (PT) under each treatment group in the Safety Analysis Set.

Where data are recorded as 'OU' (both eyes), the event will be attributed to each eye (study eye and fellow eye) in the summary table.

A listing of medical history will be generated.

7.10 Prior and Concomitant Medication

Part I and Part II

Prior medications are those that start and stop before the surgery. For control subjects, prior medications are defined as those with start and stop prior to Visit 2 (Day 0). Concomitant medications are all medications taken from the day of surgery, including those started before but ongoing at the time of the surgery (or Visit 2, Day 0 in the case of control subjects).

Prior and concomitant medications will be coded according to World Health Organization Drug Dictionary (WHODRUG) version B3 202009.

Prior and concomitant ocular medications with respect to site of administration will be presented by treatment groups, Anatomical Therapeutic Chemical (ATC) Level 4, PT and routes in the Safety Analysis Set. The ocular routes for site of administration include ophthalmic, intravitreal, subtenon, subconjunctival and potentially other peri-ocular routes. Ocular medications will be presented by study eye and fellow eye separately. Where an ocular medication is recorded as 'OU', it will be counted once for each eye (study eye and fellow eye) in the summary table.

Prior and concomitant non-ocular medication will be also presented by treatment groups, ATC Level 4, PT and routes in the Safety Analysis Set.

A subject with more than one occurrence of the same medication in a particular ATC class will be counted only once.

The oral corticosteroid treatment and tapering will be listed.

7.11 Exposure

As the treatment consists of a single injection, exposure to study medication will not be applicable.

7.12 Efficacy Analysis

7.12.1 General consideration

In Part I, efficacy endpoints will be performed using the Safety Analysis Set. For efficacy endpoints, observations collected within 6 months of the last visit window will be included in analysis. Efficacy endpoints will be summarized on observed data by descriptive statistics only. No imputation will be performed.

In Part II, efficacy endpoints will be performed using the ITT Analysis Set. For efficacy endpoints, observations collected within 6 months of the last visit window will be included in analysis.

For efficacy analysis of study eyes in Part II, descriptive analyses will be provided. Additional analyses for handling missing data will be also provided for the primary endpoint and selected secondary endpoints. For the primary endpoint regarding the proportion of eyes with improved retinal sensitivity, the primary analysis to handle missing data is the last observation carried forward (LOCF) on locus level. Then the imputed value will be dichotomized for analysis based on the responder criteria. The supplementary analyses include the non-responder imputation (NRI) imputed on locus level, and multiple imputation on locus level followed by two-sample Binomial test.

For mean change from baseline in mean sensitivity, the primary analysis to handle missing data is multiple imputation on locus level followed by the mixed model repeated measure (MMRM) analysis. For selected secondary endpoints (BCVA and LLVA) regarding their change from baseline, the primary analysis of handling missing data is the MMRM analysis. For other continuous endpoints, summaries will be made by descriptive only.

For efficacy analysis of fellow eyes in Part II, only descriptive analysis will be provided.

7.12.2 MAIA Microperimetry

General considerations for Part I and Part II

When there are more than one microperimetry exam at the same visit, the latest assessment will be used for the purpose of the analysis.

MAIA microperimetry assessment is measured in decibel (dB) using a 10-2 grid of 68 points. Each point is labeled as '< 0', '0' or a positive integer (Ref. MAIA, Microperimetry Handbook). The point labeled as '< 0' is assigned a value of '-1' by MAIA in the calculation.

Improvement in Retinal Sensitivity in center grid is defined as an increase from baseline of 7 or more decibels in any 5 or more points out of the 16 central points.

Improvement in Retinal Sensitivity in whole grid is defined as an increase from baseline of 7 or more decibels in any 5 or more points of the grid as a whole (68 points).

The proportion of eyes with improved retinal sensitivity, for both the center grid and the whole grid, will be summarized by treatment groups and visit. They will be presented by study eye and fellow eye separately. The corresponding CI may be presented by using the Clopper-Pearson method.

Mean Sensitivity in center grid is defined as the mean in dB of the 16 points located in the center of the grid.

Mean Sensitivity in whole grid is defined as the mean in dB over the whole grid (all 68 points).

Mean Sensitivity, in both the center grid and the whole grid, including change from baseline will be summarized by treatment groups, visits and eyes. The corresponding CIs for actual values at each visit are calculated by one sample t-test, and for the change from baseline are calculated by paired t-test. The 3*IQR rule method is used to identify extreme outliers for the mean sensitivity change from baseline. If a subject whose mean sensitivity change from baseline from study eye or non-study eye at every post-baseline visit is > Q3+3*IQR or < Q1-3*IQR, where Q1 is the 1st quartile, Q3 is the 3rd quartile and IQR is the interquartile range, for mean change from baseline among all post-baseline visits, this subject is regarded to have anomalous mean sensitivity data and will be excluded from analysis along with clinical judgement.

For bivariate contour ellipse area 63%, bivariate contour ellipse area 95%, P1, and P2, their observed value and change from baseline will also be summarized by treatment groups and by visits. They will be presented by study eye and fellow eye separately. The corresponding CIs will be presented by one sample t-test.

Fixation stability is defined as: if $P1 \ge 75\%$ then fixation stability is considered as stable. If P1 < 75% and $P2 \ge 75\%$ then fixation stability is considered as relatively unstable. Otherwise if P1 < 75% and P2 < 75%, then fixation stability is considered as unstable. If there are triplicates of P1 or P2 collected at a visit, the latest P1 or P2 record is selected for summary analysis. For fixation stability, shift from baseline will be summarized by shift from stable, relatively unstable, or unstable at baseline to stable, relatively unstable, or unstable at any post-baseline visit. The number and percentage of subjects within each category of fixation stability will be summarized by treatment groups and visits.

Part I

All analysis in Part I will be summarized by descriptive statistics.

The proportion of eyes with ≥ 7 dB improvement from baseline at ≥ 5 of 16 central loci, or ≥ 5 of 68 whole loci assessed by MAIA will be summarized by treatment groups, visits and eyes. The 95% CI will be calculated using the Clopper-Pearson method.

The secondary endpoint of change from baseline in mean sensitivity, in both the center 16 grid and the whole 68 grid assessed by MAIA microperimetry at 1, 2, 3, 6, 9, 12, 18 and 24 months will be summarized by treatment groups, visits and eyes. The 95% CI for mean will be calculated by one-sample t-test method, and for change from baseline will be calculated by paired t-test method.

Part II

The proportion of eyes with improved retinal sensitivity, for both the center 16 grid and the whole 68 grid will be summarized by treatment groups, visits and eyes.

Let p_{high} , p_{low} , and p_{untr} represent the proportions of eyes with ≥ 7 dB improved retinal sensitivity in 5 out of central 16 grid at Month 12 for the High Dose, Low Dose, and Untreated group, respectively.

The following 2 hypotheses will be tested:

• High Dose vs Untreated arm:

 H_{01} : $p_{high} = p_{untr}$ versus H_{11} : $p_{high} > p_{untr}$

• Low Dose vs Untreated arm:

 H_{01} : $p_{low} = p_{untr}$ versus H_{11} : $p_{low} > p_{untr}$

The proportion of eyes with improved retinal sensitivity, for both the center grid and the whole grid, at Month 12 will be compared between study arms (high dose vs untreated; low dose vs untreated) using the Fisher's Exact-Boschloo test with a Berger-Boos correction of beta=0.001 (Berger 1994). The difference in proportions between treatment groups will be presented with its corresponding 80% CI calculated using the method of Miettinen and Nurminen (Miettinen 1985).

• Primary Endpoint:

The intercurrent event is discontinuation of study early or lost to follow-up for this study. The estimand is the response rate difference between treatment and control group in ITT Analysis Set regardless of intercurrent events. The treatment policy strategy will be used for the intercurrent events. Observed data collected within 6 months outside the last visit window will be included in the analysis, including data collected after intercurrent events [ICH E9(R1) addendum 2019], i.e. discontinuation of study early or lost to follow-up.

For other missing data due to intercurrent events or other reasons, the following missing data imputation methods will be provided.

Primary analysis for missing data imputation:

The last observation carried forward method (LOCF) will be applied to the underlying continuous variables of retinal sensitivity. The imputed value will then be dichotomized based on the responder criteria, i.e., improvement of \geq 7 dB from baseline. Imputation of retinal sensitivity will be done at locus level, i.e. if a locus value is missing at a visit, the last non-missing value will be carried over to this visit.

This is a hypothetical strategy based on the assumption that the retinal sensitivity of subjects who are discontinued from the study early or lost to follow up will remain unchanged from the last observed value until the month-12 visit. This is considered a plausible assumption due to 1) the slow progression of the disease for the untreated eyes, and 2) the durability of efficacy demonstrated for the treated eyes for up to 18 months based on the current Part I data.

In addition to the primary analysis, 2 supplementary analyses are proposed under different assumptions for the estimand to assess efficacy in subjects who have missing data.

Supplementary analysis for missing data imputation:

Supplementary Analysis I:

The composite strategy will be used for the intercurrent event. The non-responder imputation method will be applied on locus level. i.e. if a locus value is missing at a visit, it will be imputed as a failure. This is a conservative approach in that any missing data will be considered as a non-responder.

Supplementary Analysis II:

The hypothetical strategy will be used with the assumption that the retinal sensitivity of the subjects who have discontinued the study early or lost to follow-up will be similar to those subjects who remain in the study. The multiple imputation approach will be applied to the missing data on the locus level under the assumption of missing-at-random (MAR). MAR assumption is considered plausible since treatment is only administered once for gene therapy after randomization in the study. Subjects do not take ongoing doses after surgery. Subjects who are lost to follow up or drop out early are not related to the effect of ongoing dose taken. These missing data are regarded missing at random. The missing retinal sensitivity data at each locus will be imputed by the method of multiple imputation. Each imputed data set will be analyzed using two-sample Binomial test. The analyzed results from the imputed dataset will be combined based on Rubin's rule (Rubin 1987) for inference assuming the statistics estimated from each imputed dataset are normally distributed.

Sensitivity analysis

It was identified that microperimetry data from one site were impacted by a protocol deviation involving assessments conducted by an unmasked rather than masked assessor from month 3 to month 12. Microperimetry is an automated test that measures the minimum luminance of a light stimulus that can be perceived by a subject at defined locus of the retina. The impact of an unmasked assessor on results is limited due to the automated nature of the test, in that the assessor is not directly involved in generating or recording the results. In addition, the perceived light stimulus at a specific locus is tested by projecting multiple stimulus points of varying light intensities. The projection strategies further reduce the probability of an unmasked assessor significantly impact the data. However, an unmasked assessor can still introduce bias into the results in indirect ways, e.g., by encouraging the subject to stay focused during the test. The risk of significantly altering microperimetry results by an unmasked assessor is believed low.

Although the risk is low, to mitigate this risk a sensitivity analysis will be implemented by excluding mean sensitivity data assessed by unmasked assessor at Part II, Month 12. The sensitivity analysis will be applied to the summaries for the proportion of eyes with mean sensitivity ≥ 7 db improvement from baseline at ≥ 5 of the 16 loci at Month 12. The sensitivity analyses will be descriptive only and analyzed on observed case. For microperimetry data in Part II, the main analysis is still based on ITT analysis set. The

sensitivity analysis will be compared with the main analysis to assess the robustness of the data.

Exploratory analysis

Secondary Endpoint:

The secondary endpoint is the change from baseline in mean sensitivity of the 16 central loci and 68 whole loci at 1, 2, 3, 6, 9 and 12 months. Observed data collected within 6 months outside the last visit window will be used regardless of intercurrent events, i.e. discontinuation of study early or lost to follow up. Observed value and change from baseline will be summarized by treatment groups, visits and eyes. The CI for observed value will be provided based on one-sample t-test, and the CI for change from baseline will be provided by paired t-test. The difference of change from baseline between treatment and control group at each visit will be provided. The CI and p-value for the difference will be also provided, which are calculated based on two sample t-test.

The primary analysis for handling missing data will be conducted by applying multiple imputation on each locus level, followed by the MMRM model under the assumption of MAR. Each imputed data set will use MMRM model to analyse change from baseline of the mean sensitivity, using fixed effects of treatment groups (high dose, low dose, and untreated), study visit, study visit-by-treatment interaction, baseline value of mean sensitivity and baseline-by-visit interaction. An unstructured covariance matrix will be used to model the within-patient variance-covariance errors. If the unstructured covariance structure matrix results are in a lack of convergence, the heterogeneous Toeplitz covariance structure followed by the heterogeneous first-order autoregressive covariance structure will be used. The Kenward-Roger approximation will be used to estimate the denominator degree of freedom. Results from analysis of each imputed dataset, i.e., least square (LS) mean differences from placebo and their SEs, will be combined using Rubin's method [Rubin 1987] as implemented in the proc mianalyze procedure to produce a pooled LS mean estimate of treatment difference, and its CI, and a nominal pooled p-value.

To account for microperimetry data from the one site impacted by unmasked assessments from month 3 to month 12, a sensitivity analysis will be implemented for central 16-loci mean sensitivity of observed value and change from baseline at Month 12, by excluding mean sensitivity data points assessed in an unmasked fashion at Month 12. The sensitivity analysis will be descriptive only and analyzed on observed case. The sensitivity analyses will be compared with analysis made by the ITT analysis set to assess the robustness of the data.

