5.2.2.3 Secondary Endpoints

- Change from baseline in microperimetry
 - Proportion of study eyes with ≥7 dB improvement from baseline at ≥5 of the 16 central loci in microperimetry at 1, 2, 3, 6 and 9 months, respectively
 - Proportion of study eyes with ≥7 dB improvement from baseline at ≥5 of the 68 loci in microperimetry at 1, 2, 3, 6, 9 and 12 months, respectively
 - Change from baseline in Mean Sensitivity of the 16 central loci at 1, 2, 3, 6, 9 and 12 months, respectively
 - Change from baseline in Mean Sensitivity of the 68 loci at 1, 2, 3, 6, 9, and 12 months, respectively

- Change from baseline in BCVA and LLVA
 - Change from baseline in BCVA and LLVA at 1, 2, 3, 6, 9, and 12 months, respectively
 - Proportion of eyes with a \ge 15 letter increase from baseline at 1, 2, 3, 6, 9, and 12 months, respectively
 - Proportion of eyes with a \ge 10 letter increase from baseline at 1, 2, 3, 6, 9, and 12 months, respectively
 - Proportion of eyes with a \geq 5 letter increase from baseline at 1, 2, 3, 6, 9, and 12 months, respectively
 - o Proportion of eyes with a ≥15 letters loss from baseline for BCVA and LLVA at 1, 2, 3, 6, 9, and 12 months, respectively
 - o Proportion of eyes with a ≥10 letters loss from baseline for BCVA and LLVA at 1, 2, 3, 6, 9, and 12 months, respectively
 - o Proportion of eyes with a ≥5 letters loss from baseline for BCVA and LLVA at 1, 2, 3, 6, 9, and 12 months, respectively
 - Proportion of eyes with change from baseline > -5 letters for BCVA and LLVA at 1, 2, 3, 6, 9, and 12 months, respectively
- Change from baseline in visual field assessed by Octopus 900 at 3, 6 and 12 months, respectively

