7 STATISTICAL METHODOLOGY

7.1 Analysis Sets

Part I

The Safety Analysis Set will consist of all subjects who receive study treatment (vitrectomy/AAV8-RPGR). The Safety Analysis Set will be used for all analyses in Part I.

Part II

The Safety Analysis Set will consist of all subjects who are randomized, under both the 2and the 3-arm randomization schedules and receive study treatment when randomized to active treatment, or attend Visit 2 (telephone call) when randomized to control (no treatment). The Safety Analysis Set will be used for safety analyses in Part II. Subjects will be analyzed based on the actual treatment they received.

The Intent-to-Treat (ITT) Analysis Set will consist of all subjects who are randomized, under the 3-arm randomization schedules. The ITT Analysis Set will be used for efficacy analyses in Part II. Subjects will be analyzed based on the treatment to which they were randomized.

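### SAP 7.12.2 lets a sustained extreme change in either eye take a subject out of the secondary mean-sensitivity analysis, with no test-quality condition, no defined reviewer and no named analysis that keeps him

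*SAP*

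**What the plan says.** SAP 7.12.2, under its considerations common to both Parts, defines an extreme subject by his own change from baseline in mean sensitivity. The change must lie above Q3 + 3×IQR or below Q1 − 3×IQR at every post-baseline visit, and either eye can trigger it. The quartiles are taken "for mean change from baseline among all post-baseline visits". The consequence is that "this subject is regarded to have anomalous mean sensitivity data and will be excluded from analysis along with clinical judgement".

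SAP 7.6 covers the same ground in different terms. It works on single data points, says "The extreme outliers may be excluded from the analysis based on statistical and clinical evaluation", promises that "The influence of the extreme outliers will be investigated", and refers to 7.12.2 for handling.

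On analysis populations, SAP 7.1 states "The ITT Analysis Set will be used for efficacy analyses in Part II" and SAP 7.12.1 repeats "In Part II, efficacy endpoints will be performed using the ITT Analysis Set". Protocol 12.3.2 agrees. None of the three makes an exception for outliers. For the other eye, SAP 7.12.1 says "For efficacy analysis of fellow eyes in Part II, only descriptive analysis will be provided".

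The endpoint concerned is secondary (SAP 5.2.2.3): "Change from baseline in Mean Sensitivity of the 16 central loci at 1, 2, 3, 6, 9 and 12 months", with a parallel endpoint for all 68 loci.

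**The concern.** Selecting subjects on the outcome being estimated undoes the protection of randomisation for that estimate. A large change present at every visit is what a faulty baseline examination would produce, since baseline is one examination (Protocol 9.1). It is also what an early and durable treatment effect would produce. The rule asks for nothing that would tell these apart, although fixation stability is summarised in the same SAP section and Protocol 10.4 names false positives and poor fixation as signs of a bad test.

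The deciding step, clinical judgement, has no criteria, no named person and no masking. The sponsor and investigators know who had surgery (Protocol 6.1.4), so masking to treated versus untreated cannot be taken for granted.

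An extreme result in the fellow eye alone can also remove the subject's study-eye data. And it is not stated whether the quartiles are pooled or separate by arm, eye, grid and Part. With about ten subjects per arm, one exclusion can shift an arm mean visibly.

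**Working it through.** **What is not affected.** The only related figure in the plan is the power of about 87% in SAP 6.6 (10 versus 9 subjects, 50% versus 5%, one-sided 0.10). Exact enumeration of the Boschloo test with the Berger-Boos correction gives 86.8%. That is the primary responder test, which the outlier rule does not touch. The plan gives no figure for the rule itself.

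**Inputs from the documents.** Arms of 10, 10 and 9 (SAP 6.6, taking 10 for each dose); six post-baseline visits (SAP 5.2.2.3); responder rates 50%/50%/5% (SAP 6.6); fences at 3×IQR (SAP 7.12.2).

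**Assumptions, because the documents give no SD.** Between-/within-subject SD of 0.5/0.5, 0.8/0.6 or 1.0/1.0 dB; normal errors; responder gain +6 dB; non-responder gain 0 dB unless stated; no missing visits; judgement never overrides the rule. Time course is either immediate (full gain from Month 1) or gradual (half at Month 1, three quarters at Month 2, then full).

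**Where the fence lies.** For normal changes with total SD σ and no responders, Q3 + 3×IQR = (0.6745 + 3 × 1.349)σ = 4.72σ.
- SD 0.5/0.5: σ = √(0.25 + 0.25) = 0.707, fence 3.34 dB
- SD 0.8/0.6: σ = √(0.64 + 0.36) = 1.00, fence 4.72 dB
- SD 1.0/1.0: σ = √(1 + 1) = 1.414, fence 6.68 dB

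A +6 dB responder must clear the fence at all six visits, so the result depends heavily on the SD. It also depends on how many subjects respond. At 50%/50%/5%, the expected responders are 5 + 5 + 0.45 = 10.45 of 29 (36%). The pooled Q3 then falls among the responders, the IQR widens, and the fence moves out of reach. At 30%/5%/5% they are 3 + 0.5 + 0.45 = 3.95 of 29 (14%), and the quartiles stay among the non-responders.

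**Simulation of the rule.** Cells show the percentage of true responders removed. Brackets show the mean Month 12 difference in dB, one dose minus control, before → after exclusion. Without exclusion the two-point model expects 0.30 × 6 − 0.05 × 6 = 1.50 dB, or 0.50 × 6 − 0.05 × 6 = 2.70 dB.

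| Setting | SD 0.5/0.5 | SD 0.8/0.6 | SD 1.0/1.0 |
|---|---|---|---|
| 50/50/5, pooled, immediate | 1.4% | 0.2% | 0% |
| 50/50/5, pooled, gradual | ≤0.03% | ≤0.03% | ≤0.03% |
| 30/5/5, pooled, immediate | 71% (1.49→0.44) | 19% (1.50→1.20) | 0.7% (1.50→1.48) |
| 30/5/5, pooled, gradual | 5.8% (1.53→1.45) | 0.7% (1.51→1.50) | 0.0% |
| 30/5/5, pooled, immediate, treated non-responders gain 0–2.19 dB | 4.0% (2.25→2.19) | 1.2% | 0.03% |
| As above, responder gains also vary (SD 1.5 dB) | 12% (2.25→2.07) | 5% | 0.5% |
| 50/50/5, within-arm quartiles, immediate | (2.69→2.92) | (2.69→2.80) | (2.68→2.70) |

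The value 2.19 dB is 5 × 7/16, the smallest average gain that meets the responder definition if the other loci do not change. Varying the gain from +4 to +8 dB in the 30/5/5 two-point setting gives 0–90% removed if immediate and 0–28% if gradual.

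The within-arm row runs the other way: it removes control responders and so enlarges the difference. Only 9 × 0.05 = 0.45 such subjects are expected per trial.

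**Faulty baseline or true gain?** In the 30/5/5 pooled setting with one control subject given a 6 dB baseline error, the rule flags him in 68%/18%/0.5% of trials across the three SDs. True responders are flagged in 54%/11%/0.3% if their gain is immediate, but 2.7%/0.4%/0.0% if gradual. The rule discriminates only when the gain builds up after Month 1.

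**Fellow-eye clause.** If one of 29 fellow eyes carries a constant baseline error, it is flagged in 44%/6%/0.1% of trials at 4 dB and 99.5%/62%/6% at 6 dB, whatever the study eye does. In an arm with 5 of 10 responders the study-eye mean is 5/10 × 6 = 3.00 dB. Losing a responder gives 4/9 × 6 = 2.67 dB; losing a non-responder gives 5/9 × 6 = 3.33 dB.

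**The case against.** The rule is narrower than a quick reading suggests. A change must be extreme at every visit, and judgement enters before anyone is dropped. Read with 7.6, the fence can be taken as nominating candidates and the evaluation as deciding. That stands as a limit on the claim, but the evaluation remains undefined, and 7.12.2 says *will* where 7.6 says *may*.

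SAP 7.6 also commits to looking at influence, which usually means results with and without the subject. The public text has gaps: in 7.12.2 a heading for exploratory analysis has nothing beneath it. So it can be said only that no such analysis is named in what is visible, not that none exists.

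The rule sits among general considerations, and the mixed-model text later in 7.12.2 does not repeat it; applying it there is reasonable but not explicit. Protocol 10.4 already allows a poor follow-up examination to be repeated. A sustained extreme change in an untreated eye can itself signal unreliable testing. That justifies a review, but not the loss of study-eye data without one.

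A reader might infer that the rule strips true responders and hides a treatment effect, or that it threatens the trial's main conclusion. The documents support neither. The primary endpoint is outside the rule, the mean-sensitivity p-values are nominal, and the large removals require assumptions the documents do not make.

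**Conclusion.** The point holds as a minor one. A secondary efficacy analysis assigned to the ITT set carries an exclusion triggered by its own outcome, in either eye, with an undefined judgement step and no named analysis that retains the subject. Sections 7.6 and 7.12.2 do not agree on how firm that exclusion is.

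The size is uncertain. With pooled quartiles at the SAP's own rates, the loss of true responders is negligible (about 1.4% or less), as it is in most other settings examined. It reaches about 70% for a +6 dB gain only when one dose has few responders, their gain is immediate, every other treated subject gains exactly 0 dB, and variability is small. Partial gains of 0–2.19 dB in treated non-responders bring that down to about 4%, or 12% if responder gains also vary. With within-arm quartiles the bias can go the other way, from about 2.70 to 2.92 dB at the smallest SD. All of this rests on assumed SDs and on judgement never overriding the rule.

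The case for change rests on the unsettled choices, which should be fixed before results are seen, and not on a demonstrated large bias.

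**What to change.** Use one wording in SAP 7.6 and 7.12.2 that flags such subjects instead of excluding them.
- Keep every ITT subject in the main Part II mean-sensitivity analysis, and repeat it without flagged subjects as a sensitivity analysis. The SAP already takes this form for the microperimetry done by unmasked assessors.
- State whether the quartiles are pooled or separate by arm, eye, grid (16 or 68 loci) and Part.
- State that a fellow-eye flag prompts review but does not by itself remove study-eye data.
- Name who reviews flagged subjects, masked to arm, using the fixation and false-positive information already available.

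The cost is SAP wording and one extra table. The drawback is that an erroneous record, such as a faulty baseline examination, stays in the main result and is dealt with only in the sensitivity table.
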